8.2. Handling BLQ Values

8.2.1. Handling of BLQ Concentrations in Summary Tables

BLQ concentrations prior to first dosing (Day 1): Pre-treatment pegcetacoplan concentrations reported as below the limit of quantification (BLQ) will be taken as zero for the computation of descriptive statistics, except geometric mean. Geometric mean cannot be calculated and will be reported as “N/A” or “-”.

BLQ concentrations occurring at any time after first dosing: Pegcetacoplan concentrations reported as below the limit of quantification (BLQ) will be taken as half the lower limit of quantification (LLOQ/2).

8.2.2. Handling of BLQ Concentrations in Figures

BLQ concentrations prior to first dosing (Day 1): Pre-treatment pegcetacoplan concentrations reported as below the limit of quantification (BLQ) will be taken as zero for linear plots, and equal to half the lower limit of quantification (LLOQ/2) for semilogarithmic plots.

BLQ concentrations occurring at any time after first dosing: Pegcetacoplan concentrations reported as below the limit of quantification (BLQ) will be taken as half the lower limit of quantification (LLOQ/2) for both linear and semilogarithmic plots.

9. PHARMACODYNAMIC ANALYSIS

9.1. Pharmacodynamic Data

Observed values, changes from baseline and percentage changes from baseline in C3, AH50, CH50, C3b/iC3b, sC5b9, C4, and C3a will be summarized at each protocol specified time point using descriptive statistics.

Individual observed values and individual changes from baseline will be presented graphically. Actual sampling times will be used for the graphical presentation of individual data. The mean (\pm SE) of the observed values, mean changes from baseline, and mean percentage changes from baseline will also be presented graphically. Nominal sampling times will be used for the mean plots.

PD parameters will be listed together with changes from baseline and percentage changes from baseline by treatment group.

In addition to the analyses outlined above, all PK and complement biomarker (PD) concentration data may be used to develop the population PK and exposure-response models in conjunction with other clinical study data. The methods and procedures will be described in a separate Analysis Plan if needed. The results from population modeling will be reported separately.

10. IMMUNOGENICITY

Immunogenicity (antidrug antibody [ADA]) data will be listed and summarized separately for anti-pegcetacoplan peptide antibody and anti-PEG antibody results using the safety set. A sample and subject level summary table will be presented as described below.

Sample Level Summary

The number of evaluable (ADA-positive, ADA-negative, and ADA-inconclusive) and unevaluable samples will be summarized by treatment group and overall. The number and percentage of each ADA sample classification will be summarized by treatment group and overall in the evaluable samples. In addition, the number and percentage of baseline and post-dose ADA positive samples along with the titer range for each will also be summarized by treatment group and overall in samples that are ADA positive. ADA positive samples will be further classified into neutralizing antibody (NAb) positive, NAb negative, or NAb inconclusive for anti-pegcetacoplan peptide antibody and summarized by treatment group and overall.

ADA samples will be classified as follows:

- ADA-Positive Sample – when the sample is positive in the confirmatory assay
- ADA-Negative Sample – when the sample is negative in the screening assay or the confirmatory assay, and drug is at a level that does not interfere with the ADA method
- ADA-Inconclusive Sample – when the sample is negative in the screening assay or the confirmatory assay, and drug is at a level that interferes with the ADA method, then the sample is considered inconclusive
- Unevaluable Sample – when a sample could not be tested for ADA status due to inadequate sample volume, mishandling, or errors in sample collection, processing, storage, etc.

Note that the drug is considered at a level that interferes with the ADA method if the corresponding visit's PK concentration is greater than or equal to: (a) 1000 ug/mL for anti-pegcetacoplan peptide antibody; or (b) 5000 ug/mL for anti-PEG antibody.

Subject Level Summary

The number and percentage of subjects with pre-existing ADAs will be summarized by treatment group and overall in the subjects with a baseline sample result. In addition, the number and percentage of subjects with an ADA positive response, ADA negative response, and ADA inconclusive response as well as the type and kinetics of the positive ADA response will be summarized by treatment group and overall in the evaluable subjects. The subject summary table will include a summary by treatment group and overall for the ADA population parameters. The subject summary table will also include the number and percentage of subjects with a positive NAb result either pre- or post-dose in the subjects with at least one pre- or post-dose sample result.

Pre-existing ADA will be defined as follows: any subject with an ADA positive baseline sample from the total subjects with a baseline sample result.

Evaluable subjects will be defined as follows: a subject with at least one sample taken with a reportable result after first dosing during the treatment or follow-up period.

Evaluable subjects will be classified as follows for ADA response:

- ADA-Positive Subject – An evaluable subject with at least one pre-dose sample and one treatment-emergent or treatment-boosted ADA-positive sample at any time after dosing
- ADA-Negative Subject – An evaluable subject without a treatment-emergent or treatment-boosted ADA-positive sample during the treatment or follow-up period
- ADA-Inconclusive Subject – An evaluable subject who cannot be classified as either ADA-positive or ADA-negative (eg, assay drug tolerance issues, post-dose positive without a baseline sample, positive baseline and positive post-dose sample without a titer value, etc.)

ADA positive responses will be classified as follows:

- Treatment-Boosted ADA Response – An evaluable subject with a baseline ADA positive sample and a post-dose ADA positive sample that is $\geq 4x$ the baseline titer (eg, baseline titer of 10 vs. post-dose titer of 40)
- Treatment-Emergent ADA Response – An evaluable subject with a baseline ADA negative sample and an ADA positive sample after treatment, ADA developed *de novo*

The kinetics of ADA positive responses will be classified as follows:

- Transient ADA Response
 - Treatment-emergent positive subjects are classified as having a transient response if they have only a single ADA positive sample (that was not the last assessment), or more than 1 ADA positive sample where the first and last ADA positive samples are separated by a period of less than 112 days (16 weeks), irrespective of any negative and positive samples in between.
 - Treatment-boosted ADA positive subjects are classified as having a transient response if they have only a single ADA boosted sample (that was not the last assessment), or more than 1 positive boosted sample where the first and last ADA positive samples are separated by a period of less than 112 days (16 weeks), irrespective of any negative and positive samples in between.
- Persistent ADA Response
 - Treatment-emergent positive subjects are classified as having a persistent response if they have more than 1 positive ADA sample ≥ 112 days (16 weeks) apart, or a positive ADA sample at the last timepoint with no further results available
 - Treatment-boosted ADA positive subjects are classified as having a persistent response if they have more than 1 positive boosted sample ≥ 112 days (16 weeks) apart, or a positive boosted sample at the last timepoint with no further results available
- Unclassified Response
 - Any ADA positive subject that cannot be defined as having a transient or persistent ADA response

ADA population parameters are derived as follows:

- ADA Prevalence – The proportion of all ADA positive subjects, including pre-existing ADA, computed as a percentage of the total number of evaluable and unevaluable subjects
- ADA Incidence – The sum of all ADA positive treatment-emergent and treatment-boosted subjects computed as a percentage of the total number of evaluable subjects

Note: This population parameter is the same as the percentage of subjects with an ADA positive response.

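### For treatment-boosted ADA with two or more boosted samples, the transient rule spans all ADA-positive samples while the persistent rule spans boosted ones, so some short boosts fall to unclassified

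*SAP*

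**What the plan says.** SAP Section 10 defines a treatment-boosted response as "An evaluable subject with a baseline ADA positive sample and a post-dose ADA positive sample" whose titer is at least 4 times the baseline titer. A sample counts as ADA positive "when the sample is positive in the confirmatory assay"; no titer condition is attached.

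The kinetics of a boosted response are then sorted by three rules:

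- **Transient** has two limbs. The first is a single boosted sample that is not the last assessment, with no condition on time span. The second is "more than 1 positive boosted sample where the first and last ADA positive samples are separated by a period of less than 112 days", whatever positive and negative results lie between.
- **Persistent** requires "more than 1 positive boosted sample ≥ 112 days (16 weeks) apart, or a positive boosted sample at the last timepoint" with no later results.
- **Unclassified** is the remainder: "Any ADA positive subject that cannot be defined as having a transient or persistent ADA response".

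The treatment-emergent transient bullet, directly above the boosted one, uses the same span wording. It suits that group, because those subjects are negative at baseline and every later positive belongs to the new response.

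**The concern.** The second transient limb and the persistent rule measure duration on different sets of samples. A boosted subject has a positive sample before the first dose and may stay positive below the 4-fold limit for the whole study. Those non-boosted positives lengthen the transient span but do not count toward the persistent test. A boost that is plainly short can therefore fail both tests.

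The label also behaves oddly as the boost lengthens. One boosted sample gives transient, and a second one two weeks later can give unclassified. At stake is the kinetics part of the subject-level immunogenicity summary, where short boosts with more than one boosted sample can drop out of the transient row.

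**Working it through.** **Inputs**

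- Threshold: 16 weeks × 7 = 112 days, which reproduces the SAP figure. Boost limit: the SAP's example, 40/10 = 4-fold.
- ADA sampling days (Protocol Table 1): Weeks 1, 2, 4, 8, 16, 24, 36, 52 = Days 1, 14, 28, 56, 112, 168, 252, 364; follow-up Weeks 54 and 60 = Days 378, 420. Protocol Table 4 agrees: 8 main-period and 2 follow-up collections.
- Baseline: the positive pre-dose sample on Day 1.
- Group 2: Protocol Table 1, note N, restricts ADA sampling in the controlled period to Group 1, so Group 2's first scheduled sample is Week 16, after dosing has begun.

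**Step 1. Worked cases (span = last day − first day)**

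| Boosted at | Other results after baseline | Boosted span | Span of all positives | Label as written | Label on boosted span |
|---|---|---|---|---|---|
| Week 2 only | positive to Week 60 | single sample | not tested | transient | transient |
| Weeks 2 and 4 | positive to Week 60 | 28 − 14 = 14 | 420 − 1 = 419 | unclassified | transient |
| Weeks 4 and 8 | positive at Week 2, negative after Week 8 | 56 − 28 = 28 | 56 − 1 = 55 | transient | transient |
| Weeks 16 and 24 | positive before, negative after | 168 − 112 = 56 | 168 − 1 = 167 | unclassified | transient |

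In the second case, stopping at Week 52 gives 364 − 1 = 363 days. Leaving out the baseline gives 420 − 14 = 406. The label is the same each way.

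**Step 2. How general this is**

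Take the 9 scheduled post-dose samples of a baseline-positive Group 1 subject, each negative, positive but not boosted, or boosted. Call a boost short when the last sample is not boosted and the first and last boosted samples are less than 112 days apart.

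- One boosted sample: 8 possible days × 2^8 results elsewhere = 2048 patterns, all transient.
- Two or more boosted samples: the days can be any 2 to 4 of Days 14, 28, 56, 112 (6 + 4 + 1 = 11 sets), or the pairs 112/168, 168/252 or 364/378. That makes 14 sets. Patterns: 9 pairs × 2^7 + 4 triples × 2^6 + 1 quadruple × 2^5 = 1152 + 256 + 32 = 1440.
- Of these 1440, with baseline counted, transient requires no positive after Day 112 (112 − 1 = 111 days). That leaves 3^4 − 2^4 − 4 × 2^3 = 33 transient and 1440 − 33 = 1407 unclassified.
- Counting post-dose positives only, 37 are transient and 1403 unclassified.
- For a subject positive at every sample, all 14 sets are unclassified on both readings.
- On the boosted span, all 1440 are transient.

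These are counts of possible patterns, not probabilities.

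**Step 3. Check of the remedy**

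The second transient limb lacks the first limb's condition on the last assessment. If only the span wording is changed, a subject boosted only at Weeks 52 and 60 has a span of 420 − 364 = 56 days and is transient, yet is also persistent because the last result is boosted. The sets 364/420, 378/420 and 364/378/420 behave this way: 2 × 2^7 + 2^6 = 320 patterns meet both rules. Requiring that the last assessment is not boosted removes all 320 and leaves no gap.

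**The case against.** The intended meaning can be recovered. The span clause follows directly on the mention of boosted samples, so its ADA-positive samples may be read as those same boosted samples. Protocol Section 10.17 points the same way: when deciding on further ADA follow-up, it treats a titer below a 4-fold increase from baseline as negative. This stands as evidence of intent. But the SAP does not carry that convention over, and its own definition of an ADA-positive sample has no titer condition. A programmer must either follow the text and produce the odd label, or depart from it.

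The consequence is also small, and that stands in full. The immunogenicity endpoint is incidence, which does not use the kinetic label. Unclassified is a predefined category, so nobody leaves the boosted count. Individual ADA data are listed.

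A reader might infer more than the text supports: that no subject with pre-existing antibody and a short boost can be transient, or that every boost confined to Weeks 2 to 8 in a continuously positive subject is mislabeled. Neither follows. A single boosted sample that is not the last is transient whatever the other results, and several boosted samples are still transient when all positives lie within less than 112 days.

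**Conclusion.** The mismatch is real but narrow. The wrong label needs all of the following: two or more boosted samples less than 112 days apart, a last assessment that is not boosted, and ADA-positive samples spanning 112 days or more once the non-boosted ones are included.

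On the schedule, Group 2 has no pre-dose sample and cannot meet the boosted definition. The reach is therefore Group 1, up to 9 subjects, and only those with pre-existing antibody. The documents do not say how many that might be. If all 9 are evaluable, one relabeled subject is 1/9 = 11.1% of the Group 1 column; with 12 evaluable overall it is 1/12 = 8.3%. Efficacy, safety and ADA incidence are unaffected, so this is a desirable correction rather than a necessary one.

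The working assumes nominal visit days and no missing samples. Visit windows of up to 7 days could move cases near the limit, since Day 1 to Week 16 is nominally 111 days. Replacing follow-up with Part B samples at Weeks 64 and 76 leaves 1407 unclassified patterns with baseline counted and 1404 with post-dose positives only.

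**What to change.** In the treatment-boosted transient bullet of SAP Section 10, make two edits to the limb for more than one boosted sample:

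1. Measure the span between the first and last boosted samples instead of the first and last ADA-positive samples.
2. Add the condition that the last assessment is not boosted.

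Both are needed. The first closes the gap, and the second keeps transient and persistent mutually exclusive. The treatment-emergent span wording can stay as it is. The cost is a minor SAP text change and a matching program change, with no effect on sampling or conduct.

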11. INTERIM ANALYSIS

No formal interim analysis is planned for this study.

12. SAFETY MONITORING COMMITTEE

A Safety Monitoring Committee (SMC) will review cumulative safety/tolerability data (e.g., physical examinations, ECGs, vital signs, clinical laboratory tests, and AEs). The SMC will have the responsibility to conduct a thorough safety assessment at regular pre-defined intervals during the treatment period of the study.

The first SMC meeting will be scheduled 4 months after the first subject is dosed with study drug and at further 4-monthly intervals until all subjects complete the Main Period. An ad hoc SMC data review may be recommended by the SMC or requested by the Sponsor at any time during the study.

The remit, roles, and responsibilities of the SMC will be specified in a separate SMC charter. There will be a separate SMC SAP covering the presentation and analyses for the SMC.

13. DATA HANDLING CONVENTIONS

13.1. General Data Reporting Conventions

All statistical analyses will be performed using SAS® (Version 9.4 or higher, SAS Institute Inc., Cary, NC, USA).

Categorical variables will be tabulated as number of subjects and percentage of total number of subjects in the given analysis set as noted for each category. Percentages will be reported to one decimal place. Descriptive statistics will be used to summarize continuous variables including number of subjects, mean, standard deviation (SD), median, Q1, Q3, minimum and maximum. Mean, Q1, Q3, and median will be reported to 1 more decimal place than the raw data, while the SD will be reported to 2 more decimal places than the raw data. Minimum and maximum will be reported the same as the original data.

Subject specific listings will be provided by treatment group, subject ID, Study Period and visit, if applicable.

13.2. Definition of Study Days

Unless otherwise noted, study days of an evaluation are defined as number of days relative to the Study Day 1 visit which is designated as Day 1, and the preceding day is Day -1, the day before that is Day -2, etc.

- For assessments on/after Study Day 1, study days are calculated as:
 - (date of assessment – date of Study Day 1 + 1)
- For assessments before Study Day 1, study days are calculated as:
 - (date of assessment – date of Study Day 1)

13.3. Definition of Baseline

For all evaluations unless otherwise noted, baseline is defined as the most recent non- missing measurement prior to the first administration of study drug (Study Day 1 for treatment group 1), or prior to/on the randomization date (Study Day 1 for treatment group 2). Baseline can be the same date as first dose, given the measurement is expected prior to first dose when only date information is available.

In by-visit summary tables, the baseline will be summarized using all available data, but also for each visit using only the baseline data from subjects with available data at the visit; hence the mean change from baseline will equal the mean visit value – mean baseline value.

Throughout this document ‘change from baseline’ refers to the actual change from baseline (i.e. visit value – baseline value).

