#### 5.2.1.2. Secondary Efficacy Endpoints

The secondary efficacy endpoints are as follows:

- The proportion of subjects with reduction in C3c staining on renal biopsy after 52 weeks of treatment
- The proportion of subjects with stabilization or improvement in estimated glomerular filtration rate (eGFR) over time
- The proportion of subjects with stabilization or improvement of serum creatinine concentration over time
- Changes from baseline biopsy in C3c staining over time
- Changes and percentage changes from baseline in eGFR and serum creatinine concentration over time

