Urine pregnancy test		X	X	X	X	X	X	X	X	X	X	X	X	X	X	X	X	X	X
FSH, HIV, HCV, HBsAg, HBcAb R	х																		
AEs	Х	X	х	Х	Х	Х	X	X	Х	Х	Х	X	Х	X	X	X	X	X	X
Post-transplant immunosuppression plan documentation		x																	
Ophthalmologic evaluation (optional) S		XS													XS				

Abbreviations: ADA = antidrug antibodies; AE = adverse events;  $\beta$ -HCG =  $\beta$ -human chorionic gonadotropin; CDC = Centers for Disease Control and Prevention;

NOTE: When multiple assessments/procedures occur at the same time, order should be: vital signs, ECGs, blood collection/sampling, pegcetacoplan dosing.

CKD-EPI = Chronic Kidney Disease-Epidemiology Collaboration; ECG = electrocardiogram; eGFR = estimated glomerular filtration rate;

FSH = follicle-stimulating hormone; GFR = glomerular filtration rate; HBcAb = hepatitis B core antibody; HBsAg = hepatitis B surface antigen;

HCV = hepatitis C; N/A = not applicable; PK = pharmacokinetic(s); RBC = red blood cell; SC = subcutaneous;

SD-OCT = spectral domain optical coherence tomography.

A. Subjects who meet the medical history requirements will enter the screening period at Visit 1 and return for Visit 2, but all Visit 2 assessments need not occur in a single visit and Visit 2 can be split into multiple visits (eg, 2a, 2b).

- B. Subjects will self-administer SC pegcetacoplan after receiving appropriate training and sign-off by a research nurse or other personnel in their first treatment week. During site visits subjects will self-administer pegcetacoplan at the site, with the exception of the very first dose. Group 2 subjects will be trained on self-administration of pegcetacoplan and receive their supply of pegcetacoplan at the next scheduled clinic visit (Visit 7 or 8) following their biopsies.
- C. Visit 2 must occur at least 7 days after Visit 1 and at least 14 days prior to the Day 1 dosing date; the vaccinations and biopsy can occur any time after confirmation of eligibility based on Visit 1 data.
- D. Specific inclusion/exclusion criteria will be measured during screening, and some of them require confirmation prior to any activities of Day 1. See the inclusion/exclusion criteria in Section 7 for further detail.

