- E. Vaccinations against N. meningitidis, S. pneumoniae, and H. influenzae are mandatory, unless documented evidence exists that subjects have received all recommended vaccines or are nonresponders to vaccination. Any required vaccines should be administered during screening (Day -14), and any required boosters should be administered at Visit 6 (Day 56), unless an alternative vaccination schedule has been agreed with the medical monitor, as described in Section 9.1.4. Subjects who withdraw from the study prior to a scheduled vaccine booster, as recommended by the current Advisory Committee on Immunization Practices adult immunization schedule, will be offered the opportunity to return to the site to receive the booster. Vaccination serum samples (for antibody titer) will be collected prior to subject receiving vaccinations on that study visit.
- F. Full physical examination will only be performed at Study Weeks -4, 1, and 52. Brief physical examinations will be conducted at all other clinic visits, as noted. A symptom-driven physical examination may be performed at other times, at the investigator's discretion. Body height (cm) will be measured during screening only and weight (kg) will be measured throughout study, during brief and full physical examinations. Edema should be assessed at every visit.
- G. Week 12 biopsy must occur at a time point between Weeks 12 and 14, inclusive; Group 2 subjects cannot begin pegcetacoplan administration until after the biopsy occurs. Week 52 biopsy must occur at a time point between Weeks 48 and 52, inclusive, but after completion of the 24-hour urine collection scheduled for Week 48.
- H. Between site visits, subjects will be instructed to report any infusion site reaction to the study staff. Pump use safety assessment will be performed by licensed health care professional (ie, investigator or nurse) within 30 minutes following study drug administration at all clinic visits and during at-home qualification. See Manual of Procedures for more details.

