## 9.1.3. Renal Biopsy

The screening renal allograft biopsy should be conducted during the screening period and must occur within 4 weeks leading up to the day of randomization. However, a nonstudy biopsy may be used as the screening biopsy provided it meets all the following criteria:

- it was performed no more than 12 weeks prior to Week 1
- the subject has remained clinically stable since the biopsy with no changes in medication regimens that would be expected to significantly alter the screening renal allograft biopsy findings
- the prior biopsy is available for central pathology review and includes all the required components of a study screening renal allograft biopsy

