1. INTRODUCTION

This statistical analysis plan (SAP) provides a technical and detailed elaboration of the statistical analyses of efficacy, safety, and pharmacokinetic/pharmacodynamic data as described in the study protocol Amendment 3 dated 03 February 2022. Specifications for tables, figures, and listings are contained in a separate document.

There are two parts of this study: Part A includes an approximate 8-week screening period to be followed by a 52-week main period, during which time Group 1 will have pegcetacoplan administration for all 52 weeks and Group 2 will receive pegcetacoplan administration only following the Week 12 biopsy through the remainder of the main period. All subjects then enter the 8-week follow-up period or the long-term extension (Part B).

The total duration of participation is up to 68 weeks (not including the Part B long-term extension).

For analysis purposes, data will be summarized by treatment groups and overall. When applicable (and it will be specified in the following sections), the summary tables will be further separated by the 3 treatment phases (Part A Controlled Portion, Part A Noncontrolled portion, and Part B long-term extension) and combined.

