3.5. Analysis Timing

The analysis of data from the Part A Controlled Portion of the study will be performed when all subjects have completed the Part A Controlled Portion or discontinued early and all corresponding data have been entered into the database, reviewed, cleaned, and finalized, and the Week 12 Analysis database locked. At that time, the primary analysis will be performed, which will include all efficacy and safety analyses for the Part A Controlled Portion. For Week 12 Analysis, all summary tables will be presented by randomized group.

The analysis of data from the Part A Non-Controlled Portion will be performed once all subjects have completed the Part A Non-Controlled Portion or discontinued early and all corresponding data have been entered into the database, reviewed, cleaned, and finalized, and the Week 52 Analysis database locked. For disposition, baseline summary, and efficacy analysis, tables will be presented similarly as Week 12 Analysis.

The table summaries for protocol deviations, concomitant medications, study drug exposure and compliance, as well as all AE summaries will be presented in 5 columns: (1) Group 1's Part A Controlled Portion results; (2) Group 1's Part A Non-Controlled Portion results; (3) Group 2's Part A Non-Controlled Portion results; (4) Part A Non-Controlled Portion results combined (in other words, combining columns 2 and 3); (5) for all results since Pegcetacoplan injection (in other words, combining columns 1 and 4). More details on the summary layout are provided in the separate table shell document.

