6. EFFICACY ANALYSIS

6.1. Analyses of Primary Efficacy Endpoint

The primary efficacy endpoint is the proportion of subjects with reduction in C3c staining on renal biopsy at Week 12.

The baseline renal allograft biopsy will be taken as defined per Protocol Section 9.1.3.

The proportion of subjects with reduction in C3c staining at Week 12 will be tabulated, along with the 95% confidence intervals (CIs).

Categories for C3c staining are: 0 (including negative and trace), 1, 2, 3, and NA (meaning no C3c staining available or no glomeruli in the sample stained for C3c). Reduction in C3c staining is defined as decrease of at least 2 orders of magnitude of intensity from baseline (e.g., baseline result being 3 and Week 12 result being 1 or 0). Missing or NA results at Week 12 will be listed separately. A composite strategy will be used for addressing intercurrent events. The C3c staining status at or after the initiation of any of intercurrent events, including but not limited to, the use of prohibited concomitant medication, starting renal replacement therapy due to worsening of underlying disease, use of rescue therapies, premature withdrawal from the treatment, will be regarded as non-reduction. The initiation of intercurrent events will be reviewed by medical team and provided to biostatistics team.

Sensitivity analysis such as using treatment policy strategy for handling intercurrent events, meaning that Week 12 C3c staining status will be collected and analyzed regardless of an intercurrent event has occurred or not, will also be performed. Supportive analysis may be conducted based on those who have both baseline and Week 12 C3c staining results.

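### Group 2's change to Week 52 is measured only from a pre-randomization baseline, so it mixes about 12–14 untreated weeks with treated time, and the wording of 52 weeks of treatment cannot hold for that group

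*SAP*

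**What the plan says.** - **Baseline.** SAP 13.3 applies unless a section says otherwise. Group 1 is measured from the last value before first dose; for Group 2 the rule is "or prior to/on the randomization date (Study Day 1 for treatment group 2". For C3c, SAP 6.1 sets its own rule: "The baseline renal allograft biopsy will be taken as defined per Protocol Section 9.1.3". That protocol section asks for a biopsy in the 4 weeks before randomization, or accepts a non-study biopsy on conditions that include "it was performed no more than 12 weeks prior to Week 1". Protocol 12.3.3 also takes the exploratory baseline before randomization.
- **Start of drug in Group 2.** Dosing follows the Week 12 biopsy, which is allowed from Week 12 to Week 14. Table 1 footnote B has these subjects receive their supply "at the next scheduled clinic visit (Visit 7 or 8) following their biopsies".
- **Final biopsy.** Table 1 footnote G: "Week 52 biopsy must occur at a time point between Weeks 48 and 52, inclusive".
- **Endpoint wording.** Protocol 5.2.1.2 has "The proportion of subjects with reduction in C3c staining on renal biopsy after 52 weeks of treatment", with no restriction by group. Protocol 12.3.2 and SAP 2.2.2 agree. The proteinuria remission endpoint (Protocol 5.2.1.3, SAP 2.2.3) is also worded by weeks of treatment. SAP 6.2 and 6.3 instead tabulate both at Week 52, and SAP 15 records no change from the protocol.
- **Layout.** SAP 3.5 presents the Week 12 tables by randomized group and then says: "For disposition, baseline summary, and efficacy analysis, tables will be presented similarly as Week 12 Analysis". SAP 1 gives the general rule that "data will be summarized by treatment groups and overall". For adverse events, exposure, deviations and concomitant medications, SAP 3.5 specifies five columns aligned to exposure, including Group 2 in the noncontrolled portion alone and everything since first pegcetacoplan.

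**The concern.** Group 2 passes through two treatment states, but its efficacy has one baseline, set before both. A change from that baseline to Week 52 is the sum of whatever happened untreated and whatever happened on drug. The trial obtains the values needed to separate the two: a Week 12 biopsy that must precede first dose, and pre-dose laboratory values at Visit 7 or 8 (Protocol 9.2.3.1). No planned efficacy summary uses them as a starting point, although the adverse event tables already separate the two states.

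At stake is the secondary objective, the effect after 52 weeks of treatment. A Group 2 subject could count as a Week 52 responder on a change that occurred before any drug, or as a non-responder despite a full response on drug. The endpoint wording would also describe an exposure that no Group 2 subject has in the main period.

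**Working it through.** **Inputs.** Protocol Table 1: Week 12 = Day 84, Week 14 = Day 98, Week 48 = Day 336, Week 52 = Day 364; Visits 7, 8 and 16 have ±7 days. SAP 6.1: reduction means a fall of at least 2 grades on a 0–3 scale. Eligibility requires at least 2+ on the screening biopsy. SAP 6.2: eGFR is stable or improved if it falls by no more than 25%.

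**The plan's own figures.** Noncontrolled portion: 52 − 12 = 40 weeks, as in SAP Figure 1. Total participation: 8 + 52 + 8 = 68 weeks, as in SAP 1. Both reproduce.

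**Untreated time in Group 2.** (84 − 1)/7 = 11.9 to (98 − 1)/7 = 13.9, so about 12–14 weeks. That is 12/52 = 23% to 14/52 = 27% of the main period. With visit windows, (77 − 1)/7 = 10.9 to (105 − 1)/7 = 14.9. For C3c, the gap from baseline biopsy to first dose can reach 4 + 14 = 18 weeks, or 12 + 14 = 26 with a non-study biopsy.

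**Group 2 time on drug**

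| Point | Nominal | Variants |
|---|---|---|
| Week 52 biopsy | (336 − 98)/7 = 34 to (364 − 84)/7 = 40 weeks | Visit 8 at +7 days: (336 − 105)/7 = 33; ±7 days at both ends: 32–42 |
| Week 52 laboratory visit | (364 − 98)/7 = 38 to (364 − 84)/7 = 40 weeks | ±7 days at both ends: 36–42 |

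Protocol 8.2 instead has Group 2 dosing begin no earlier than Week 13, which gives 48 − 13 = 35 to 52 − 13 = 39 weeks at the biopsy. That statement and footnote B need reconciling, but the conclusion is the same under either. Against 52 weeks, the nominal shortfall at biopsy is 12 to 18 weeks (23% to 35%). Group 1 at the same biopsy has (336 − 1)/7 = 47.9 to (364 − 1)/7 = 51.9 weeks.

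**Effect on C3c responder status.** Write a course as screening / Week 12 pre-dose / Week 52. With screening grade 2 or 3 and later grades 0–3 there are 2 × 4 × 4 = 32 courses. Status differs between the two baselines in 8:

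- Responder from screening only (7): 2/0/0, 2/1/0, 3/0/0, 3/0/1, 3/1/0, 3/1/1, 3/2/1.
- Responder from pre-dose only (1): 2/3/1.

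Of the 7, four show no fall on drug (2/0/0, 3/0/0, 3/0/1, 3/1/1) and three show a one-grade fall. Six of the 7 start drug at grade 0 or 1, where a 2-grade fall is impossible. These are counts of possible courses, not probabilities.

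**Effect on eGFR, both directions (illustrative values).** 100 to 80 untreated, then 72 on drug: (72 − 100)/100 = −28%, not stable, against (72 − 80)/80 = −10%, stable. 100 to 110 untreated, then 82 on drug: −18%, stable, against (82 − 110)/110 = −25.5%, not stable.

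**The case against.** The strongest reply is that nothing here is an error. Efficacy is analysed on all randomized subjects, by randomized group and without hypothesis tests. For immediate against delayed start, a common pre-randomization baseline is a legitimate choice, and a pre-dose baseline answers a further question. The SAP sections that define the tables say Week 52, not weeks of treatment. A C3c spaghetti plot is planned, and with at most 3 Group 2 subjects a course such as 3/1/1 would be visible. Pooling is not established either: the overall summary is a general rule, SAP 3.5 places efficacy by randomized group, and the table shells are a separate document.

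Most of this stands. A reader might infer that the SAP counts untreated weeks as drug effect, or that it will report Group 2 as treated for 52 weeks. The documents do not support that: the SAP makes no such attribution, and its analysis sections use study time. Nor is the crossover the only within-subject comparison of off and on drug, since Group 1 also has untreated baseline values.

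The reply does not close the gap. The plot covers C3c only and gives neither a pre-dose change nor a responder status. In a descriptive study of up to 12 subjects, the tabulated proportions are the result. The two wordings of the endpoint remain unreconciled.

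**Conclusion.** The point holds as a gap in the Week 52 efficacy summaries and an unreconciled endpoint wording. Group 2's change to Week 52 includes about 12–14 untreated weeks, with longer gaps possible for C3c, and can mislead in either direction. The wording of 52 weeks of treatment cannot apply to a group with nominally 34–40 weeks on drug at biopsy and 38–40 at the laboratory visit.

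The size is modest: up to 3 of 12 subjects, and secondary and exploratory descriptive endpoints only. One subject is 1/3 = 33 points of Group 2 and 1/12 = 8 points of an overall result. That shows the scale of one reclassification; it does not measure bias. The primary Week 12 comparison is unaffected, and the randomization baseline is right for it.

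The exposure figures rest on the nominal visit days, with first dose at Visit 7 or 8. How often responder status would actually differ cannot be known from the documents.

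**What to change.** - Keep the randomization baseline for the Week 12 comparison, and keep the efficacy tables by randomized group.
- In SAP 6.1–6.3 and 13.3, add a supplementary Group 2 summary for the noncontrolled portion. Measure from the last value before first pegcetacoplan: the Week 12 biopsy for C3c and histology, and the pre-dose Visit 7/8 value for eGFR, creatinine and uPCR. Present it by actual time since first dose.
- For C3c, give each subject's grade change beside responder status, because of the floor at pre-dose grade 0–1.
- Label the results as at Week 52, with actual weeks of exposure for each group. Reconcile the endpoint wording in Protocol 5.2.1.2, 5.2.1.3, 12.3.2 and 12.3.3 and SAP 2.2.2–2.2.3 with SAP 6.2–6.3. Do not describe a pooled Week 52 column as 52 weeks of treatment.
- If Week 64 (Day 448) is used for Group 2, nominally (448 − 98)/7 = 50 to (448 − 84)/7 = 52 weeks on drug, label it as limited to Part B entrants. They are selected for benefit as judged by the investigator.

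The cost is one more baseline definition and one small table set for up to 3 subjects, from data already collected. No new visits or biopsies are needed.
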